**Table 2: World Health Organization Ordinal Scale for COVID-19**

Patient State	Description	Score
Uninfected	No clinical or virological evidence of infection	0
Ambulatory	No limitation of activities	1
	Limitation of activities	2
Hospitalized, Mild Disease	Hospitalized, no oxygen therapy	3
	Oxygen by mask or nasal prongs	4
Hospitalized, Severe Disease	Noninvasive ventilation or high-flow oxygen	5
	Intubation and mechanical ventilation	6
	Ventilation + additional organ support – pressors, RRT, ECMO	7
Dead	Death	8

Abbreviations: ECMO = extracorporeal membrane oxygenation; RRT = renal replacement therapy

6. Proportion of patients who develop critical COVID-19 illness as defined by at least one of the following:
  - A. RF defined based on resource utilization requiring at least one of the following: Endotracheal intubation and mechanical ventilation, oxygen delivered by high-flow nasal cannula (heated, humidified, oxygen delivered via reinforced nasal cannula at flow rates > 20 L/min with fraction of delivered oxygen  $\geq 0.5$ ), noninvasive positive pressure ventilation, ECMO, clinical diagnosis respiratory failure (i.e., clinical need for one of the preceding therapies, but preceding therapies not able to be administered in setting of resource limitation)
  - B. Hemodynamic compromise (defined by systolic blood pressure < 90 mm Hg, or diastolic blood pressure < 60 mm Hg or requiring vasopressors)
  - C. Multi-organ dysfunction/failure
7. Time to clinical improvement from baseline value (defined by time to  $\geq 1$ -point improvement on the WHO Ordinal Scale for COVID-19 score – must be maintained through Day 28)
8. Mean change from baseline in WHO Ordinal Scale for COVID-19 score at Day 14/EOT, Day 28, Day 57
9. Incidence and duration of intubation
10. Length of intensive care unit stay
11. Incidence and duration of supplemental O2 administration
12. Incidence and duration of noninvasive ventilation or high-flow nasal cannula O2 administration
13. Incidence and duration of mechanical ventilation
14. Incidence and duration of mechanical ventilation plus additional organ support using vasopressors, and/or renal replacement therapy and/or ECMO
15. Daily ratio of oxygen saturation (SpO2) to fractional inspired O2 (SpO2/FiO2)
16. Length of hospital stay
17. Incidence of re-hospitalization through Day 57
18. Proportion of subjects requiring intensive care unit admission post randomization

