After signing informed consent, patients will be screened upon presentation at the hospital. Screening will include full physical examination, vital signs, safety laboratory evaluation, oxygen (O_2) saturation, pre-diagnostics to measure prostaglandin D2 (PGD2) status, and baseline assessment of World Health Organization (WHO) Ordinal Scale for COVID-19 that is derived from O_2 supplementation requirements. If confirmed that they qualify for this protocol according to listed inclusion and exclusion criteria, patients will receive their first dose of investigational medicinal product (IMP). They will then receive IMP PO or NG (if intubated or unable to swallow medication) once daily, at approximately the same time each day for up to 13 additional days. IMP will be administered in addition to standard of care deemed appropriate by the treating physician(s). Patients will be randomized to receive asapiprant or placebo in a blinded manner. Patients will be monitored daily for all relevant efficacy outcomes, O_2 saturation and adverse events (AEs). Blood will be drawn periodically for safety laboratory measurements, plasma kinetics, lymphocyte subsets, CRP, and cytokines (see protocol, Table 1 Schedule of Assessments). Nasopharyngeal swabs will be collected to measure viral load. Patients will be monitored at follow-up visits on Day 28 (approximately 14 days after the last dose) and Day 57 (approximately 43 days after last dose).

Treatment Period

Each patient will participate in the study for approximately 8 weeks from the time the patient signs the informed consent form (ICF) through the final contact. After screening, each patient will receive, daily, 1 dose of assigned treatment between Day 1 and Day 14. The WHO Ordinal Scale for COVID-19 will be derived daily while hospitalized, at Day 14, and at follow-up visits until the patient has completed the study.

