7. Time to clinical improvement from baseline value (defined by time to ≥ 1 -point improvement on WHO Ordinal Scale for COVID-19 score – must be maintained through Day 28)
8. Mean change from baseline in WHO Ordinal Scale for COVID-19 score at Day 14/End of Treatment, Day 28, Day 57
9. Incidence and duration of intubation
10. Length of intensive care unit stay (ICU)
11. Incidence and duration of supplemental O₂ administration
12. Incidence and duration of noninvasive ventilation or high-flow nasal cannula O₂ administration

13. Incidence and duration of mechanical ventilation
14. Incidence and duration of mechanical ventilation plus additional organ support using vasopressors, and/or renal replacement therapy and/or ECMO
15. Daily ratio of oxygen saturation (SpO_2) to fractional inspired O_2 ($\text{SpO}_2/\text{FiO}_2$)
16. Length of hospital stay
17. Incidence of re-hospitalization through Day 57
18. Proportion of patients requiring intensive care unit admission post randomization

Exploratory Endpoints

1. Inflammation markers including: IL-6, CRP, IL-10, TNF- α , IFN- γ , IFN- α , IP-10, MCP-1, and absolute lymphocyte count
2. Assess peak and trough concentrations of asapiprant at steady state
3. Assess PGD2 pre-diagnostic to assess correlation with response to treatment for COVID-19 based on change in the WHO Ordinal Scale for COVID-19 score

Safety endpoints

1. Incidence and severity of treatment-emergent AEs (TEAEs)
2. Safety outcome measure:
 - a. Occurrence of AEs
 - b. Laboratory safety parameters such as complete blood count, blood glucose, electrolyte, hepatic and renal functions taken before the first dose and on Days 2, 5, 14 and 28 and the time of discharge to find any changes or any systemic effect after treatment

3 Analysis Sets

Enrolled Analysis Set: all patients who provided informed consent.

Intent-to-Treat (ITT): all patients who have been randomized. The ITT will be used for efficacy endpoints. Patients will be analyzed according to the treatment group to which they were randomized. The ITT will be used for the primary efficacy analysis.

Modified Intent-to-Treat population (mITT): all ITT patients with exclusion of randomized untreated patients and randomized ineligible patients.

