4.4 Missing Data

In general, missing data will not be imputed except partial and missing dates as specified below. The data will be analyzed as they are recorded.

Details of handling missing primary endpoint are addressed in section [10.1](#) primary analysis.

WHO Ordinal Scale for COVID-19 scores will be analyzed by carrying forward any early deaths to Day 28.

Partial or missing dates and times

The missing component(s) of incomplete dates (e.g., start and/or stop dates of AE, concomitant medication, medical history) will be assumed as the most conservative value possible. For example, if the start date has a missing day value, the first day of the month will be imputed for study day computations, etc. If day is missing for an end date, the last day of the month will be imputed. If the start date has a missing month value, the first month of the year will be imputed for study day

QMS Document Name: Statistical Analysis Plan	Page 13 of 27
QMS No (include version ref): STF-015-GL.02	Document date: 09JUL2019
CONFIDENTIAL	

computations, etc. If month is missing for an end date, the last month of the year will be imputed. For determination of treatment-emergent status, the start date will be imputed as the date of the first dose of study drug, unless there is clear evidence (through comparison of partial dates/times) to suggest otherwise.

Date imputation will only be used for computational purposes such as treatment-emergent status, etc. Actual date values, as they appear in the original electronic case report forms (eCRFs), will be presented in the patient data listings.

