10.2.2 Time to event endpoints

Following time to event endpoints will be presented by treatment group, using the Kaplan-Meier estimator. A Cox proportional hazards model with treatment, previous COVID-19 therapy (yes/no), region, and age group (50 to < 75 vs. ≥ 75 years of age) as covariates will be used to estimate the hazard ratio and compare treatment groups. In addition, the log rank test and stratified log rank test, with age group and region as the strata, will be provided.

- Time to two successive negative viral titers in nasopharyngeal swab: which is defined as time from the date of randomization to the date of second post-dosing viral titers collection with negative result of two successive negative viral titers tests. If a patient doesn't have documented two successive negative viral titers, it will be censored at the date of Day 28 or date of discontinuation from study, which ever comes earlier.
- Time to clinical worsening from baseline value (defined by time to ≥ 1 -point worsening on WHO Ordinal Scale for COVID-19): which is defined as time from the date of randomization to the date of first post-dosing collection of WHO Ordinal Scale for COVID-19 showing higher than baseline, i.e., ≥ 1 -point worsening. If a patient doesn't have documented worsening post-baseline WHO Ordinal Scale, it will be censored at the date of Day 57 or date of discontinuation from study, which ever comes earlier.
- Time to clinical improvement from baseline value (defined by time to ≥ 1 -point improvement on WHO Ordinal Scale for COVID-19 score – must be maintained through Day 28): which is defined as time from the date of randomization to the date of first post-dosing collection of WHO Ordinal Scale for COVID-19 showing a decrease from baseline, i.e., ≥ 1 -point decrease demonstrating clinical improvement. If a patient doesn't have documented improving post-baseline WHO Ordinal Scale, it will be censored at the date of Day 28 (including death prior to Day 28) or date of discontinuation from study, whichever comes earlier.

10.2.3 Mean change in WHO Ordinal Scale for COVID-19 score at Day 14/End of Treatment, Day 28, Day 57

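### SAP 10.2.2 contradicts itself on time to clinical improvement: the label requires the improvement to last to Day 28, but the derivation and censoring rule count the first 1-point fall

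*SAP*

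**What the plan says.** Secondary endpoint 7 is time to clinical improvement. Protocol 2.3.2 (below Table 2) asks for at least a 1-point "improvement on the WHO Ordinal Scale for COVID-19 score – must be maintained through Day 28". The protocol synopsis and SAP 2.3 carry the same condition.

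SAP 10.2.2 first restates the condition in the endpoint's label. The derivation that follows starts the clock at randomization and runs it "to the date of first post-dosing collection of WHO Ordinal Scale for COVID-19 showing a decrease from baseline". Its censoring rule begins "If a patient doesn't have documented improving post-baseline WHO Ordinal Scale, it will be censored at the date of Day 28". A parenthesis adds deaths before Day 28, and discontinuation is the censoring date if it comes earlier.

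Three other provisions bear on the point:
- SAP 4.4: "WHO Ordinal Scale for COVID-19 scores will be analyzed by carrying forward any early deaths to Day 28".
- SAP 2 (Treatment Period): the score is "derived daily while hospitalized, at Day 14, and at follow-up visits".
- Protocol 8.4 leaves censoring rules for time-to-event endpoints to the SAP, and SAP 1 says that the SAP prevails where the two documents differ.

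**The concern.** The event date depends on one score, the first post-dose value below baseline, and no later score is consulted. The censoring rule is triggered only when there is no improvement on record. A patient whose scores run 4, 3, 6, death has an improvement on record, so the literal rule makes that patient an event on the day of the 3. The provision for deaths before Day 28 does not reach the patient, because it sits inside the rule for patients who never improved.

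The endpoint's own definition says the opposite: this patient did not keep the improvement. Nowhere do the documents say how to treat a patient who improves and then loses it, or which date counts if improvement recurs. Because the protocol defers to the SAP on censoring, nothing else fills the gap.

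At stake is an endpoint that could count some treatment failures as successes and date other successes too early.

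**Working it through.** The plan states no figure for this endpoint, so there is none to reproduce. The check compares the two rules on example paths and then illustrates the size.

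**Step 1. Two rules, four invented paths, baseline score 4.**

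| Path | Derivation as written (first score below 4) | Condition in the label (below 4 at every later score through Day 28) |
|---|---|---|
| 3 on Day 3, RF on Day 8, death on Day 12 | event, Day 3 | censored, Day 28 |
| 3 on Day 3, back to 4 on Day 5, discharged Day 15 and stays improved | event, Day 3 | event, Day 15 |
| 3 on Day 5, improvement kept | event, Day 5 | event, Day 5 |
| never below 4 | censored, Day 28 | censored, Day 28 |

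The rules differ for the first two paths: a failure becomes a success in one, and the date moves by 12 days in the other. Carrying a death forward does not repair the first path, because the literal rule stops at Day 3.

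**Step 2. Comparison with neighbouring bullets.** In the same section, the viral-titer endpoint builds its condition into the derivation: the event is dated at the second of two successive negatives. The improvement bullet instead mirrors the worsening bullet, which uses the first qualifying score and has no maintenance condition.

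**Step 3. Can such paths occur?** Baseline scores are 3 or 4 (SAP 4.3). From 4, one assessment off oxygen while still in hospital gives a 3, which qualifies. Scores are derived daily in hospital, so short falls would be recorded. The SAP Addendum reports no RF among subjects with baseline 3 in the blinded data, so the route through RF is confined to baseline 4.

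**Step 4. Illustrative size.** Inputs: planned failure rates of 31% (placebo) and 15% (asapiprant), and 312/2 = 156 per arm (Protocol 8.6, SAP 2.2). Assumptions not in the documents: a share f of failures had an earlier transient fall, f is the same in both arms, and every non-failure improves and stays improved.

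- Difference in proportion improved under the label: 85% − 69% = 16.0 points.
- Failures counted as improved: 0.31 × f on placebo and 0.15 × f on asapiprant.
- Points lost: (0.31 − 0.15) × f = 0.16 × f.

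| f (assumed) | Placebo failures counted as improved | Asapiprant failures counted as improved | Points lost | Difference left |
|---|---|---|---|---|
| 10% | 3.1% (4.8 of 156) | 1.5% (2.3) | 1.6 | 14.4 |
| 20% | 6.2% (9.7) | 3.0% (4.7) | 3.2 | 12.8 |
| 30% | 9.3% (14.5) | 4.5% (7.0) | 4.8 | 11.2 |
| 50% | 15.5% (24.2) | 7.5% (11.7) | 8.0 | 8.0 |

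**Step 5. Direction.** If the shares differ by arm, the points lost are 0.31 × f(placebo) − 0.15 × f(asapiprant). This turns negative, so that the difference is inflated, once f(asapiprant) exceeds 0.31/0.15 = 2.07 times f(placebo).

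**The case against.** The strongest reply is that the SAP has not dropped the condition. It stands in the same bullet, in text that is itself definitional, and again in SAP 2.3. On that reading the derivation only says which date to use once improvement in the labelled sense is established. The reference to documented improvement in the censoring rule would then also mean maintained improvement, and the provision for deaths would reach a patient who dies after a brief fall. This much stands: a reader might infer that the SAP abandons the condition, and it does not. The defect is a conflict between label and derivation. But the favourable reading still gives no date for an improvement that is lost and regained.

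A reader might also infer that the programmed analysis miscounts these patients. SAP 1 places table specifications and any example code in a separate document that is not available here, so what was programmed is unknown.

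The size is open to objection too. The share f is assumed, and taking it as equal across arms fixes the direction. The illustration uses proportions, whereas SAP 10.2.2 plans Kaplan-Meier, Cox and log-rank analyses, and no effect on the hazard ratio was calculated. The failure rates are planning values, and the Addendum says that enrollment stopped before the interim analysis. All of this stands.

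Finally, this is one of 18 secondary endpoints. Protocol 8.4 designates none as key and applies no multiplicity correction.

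**Conclusion.** The point holds as an internal contradiction in SAP 10.2.2. Taken literally, the derivation and censoring rule give a result contrary to the endpoint's definition in the label, in SAP 2.3 and in the protocol. This rests on the wording alone and needs no assumption about rates.

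The effect on the treatment comparison is conditional. With a similar share of transient improvers among failures in both arms, it runs towards no difference: about 1.6 to 8.0 points of the difference in proportion improved for an assumed 10% to 50% at 31% and 15%. A firm statement that the result is biased towards no difference, or by a given amount, is not supported, because the documents give no share by arm and the planned analysis is time-to-event.

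The primary endpoint, the sample size and the interim rule are unaffected. The correction is worth making because the rule as written can score a death as an improvement and the scores needed are already scheduled.

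**What to change.** Before unblinding, replace the derivation and censoring text for this endpoint in SAP 10.2.2 so that it says:

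- The event date is the first post-dosing assessment from which every available WHO score through Day 28 is at least 1 point below baseline, with death scored 8 and carried forward to Day 28.
- A patient who loses the improvement, regains it and keeps it through Day 28 is an event at the start of that final maintained improvement.
- A patient who loses it and does not regain it through Day 28, or who dies by Day 28, is censored at Day 28. For deaths this extends the SAP's existing rule to those who improved first.
- How patients who improve and then discontinue before Day 28 are handled. A rule based only on available scores would count them as events unless the SAP says otherwise.
- How days without a score after discharge are handled, since maintenance is then judged on fewer assessments.

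The table specifications and code should be checked against the new text. If unblinding has already taken place, the choice should be reported as a change from the SAP with its rationale, as SAP 1 requires.

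Cost: a short SAP revision and no new data. The downside is fewer or later improvement events, and so somewhat less information for this endpoint.

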10.2.4 Other continuous secondary efficacy endpoints

Following continuous endpoints will be analyzed using an analysis of covariance (ANCOVA) model, with treatment as a fixed effect and baseline WHO Ordinal Scale score, age group (50 to < 75 vs. ≥ 75 years of age) and region. Results from Wilcoxon rank sum test and t-tests will also be reported. The ITT and PP analysis (if formed) sets will be used for these exploratory subset analyses.

- Duration of intubation: which will be defined as duration of first post-dosing intubation based on start and end date of the intubation.

QMS Document Name: Statistical Analysis Plan	Page 21 of 27
QMS No (include version ref): STF-015-GL.02	Document date: 09JUL2019
CONFIDENTIAL	

- Length of intensive care unit (ICU) stay in days which will be defined as duration of first post-dosing ICU stay based on start and end date/time of the stay.
- Duration of supplemental O₂ administration in days : which will be defined as duration of first post-dosing supplemental O₂ administration based on start and end date/ of the O₂ administration.
- Duration of noninvasive ventilation or high-flow oxygen therapy in days: which will be defined as duration of first post-dosing noninvasive ventilation or high-flow oxygen therapy based on start and end date/time of the noninvasive ventilation or high-flow oxygen therapy.
- Duration of mechanical ventilation in days: which will be defined as duration of first post-dosing mechanical ventilation based on start and end date/time of the mechanical ventilation.
- Duration of mechanical ventilation plus additional organ support using vasopressors, and/or renal replacement therapy and/or ECMO: which will be defined as duration of first post-dosing mechanical ventilation plus additional organ support using vasopressors, and/or renal replacement therapy and/or ECMO based on start and end date/time of the mechanical ventilation plus additional organ support using vasopressors, and/or renal replacement therapy and/or ECMO.
- Daily ratio of oxygen saturation (SpO₂) to fractional inspired O₂ (SpO₂/FiO₂): which will be defined as SpO₂/FiO₂ as collected in CRF. The ratio will be analyzed for each day with the value being collected. If FiO₂ was not collected for some O₂ delivery methods, following guide can be followed to convert O₂ flow rate to FiO₂.

O ₂ delivery method	O ₂ flow rate (l/min)	Estimated FiO ₂
Nasal cannula ("NASAL CANNULA LARGE TUBING" and "NASAL CANNULA TRADITIONAL TUBING")	1	24
	2	28
	3	32
	4	36
	5	40
	>=6	44
Nasopharyngeal catheter	1	25
	2	30
	3	35
	4	40
	5	50
	>=6	60
Face mask (simple mask)	<5	Follow nasal cannula
	5	40
	6-<7	50
	>=7	60

Face mask with reservoir (non-rebreather face mask)	<6	Follow nasal cannula
	6	60
	7	70
	8	80
	9	90
	10	95
	>10	100
Venturi mask	1	22
	2	24
	3	26
	4	28
	6	31
	8	40
	10	50
	>10	60

In case of fractional value of flow rate (0.5, 1.5, 2.5, 3.5, 4.5), $\text{FiO}_2 = (\text{Oxygen Flow Rate} * 4) + 20$ to avoid rounding.

- Length of hospital stay, after start of study treatment, in days: which will be defined as duration from date of randomization to the date of first discharge.

11 Safety

All safety endpoints will be analyzed using the SAF under received treatment based on the data observed. No missing data will be imputed.

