**Table 1: Schedule of Assessments**

	Screening	Baseline	Treatment													Time of Discharge a	28-Day Follow-up	End of Study Follow-up
Study Day (Window)	Day -3 to -1	Day 1	2	3	4	5 + 2	6	7	8	9	10	11	12	13	14/ EOT + 2		Day 28 (±2 days)	Day 57 (±4 days)
Informed consent	X																	
Inclusion/exclusion criteria review	X	X																
Medical history/ demographics	X																	
Physical examination b	X																	
Abbreviated physical examination b					X										X	X	X	
Vital signs b	X	X	X	X	X	X	X	X	X	X	X	X	X	X	X	X	X	
Prior medication review	X																	
Safety laboratory tests	X i		X		X										X	X	X	
O 2 Saturation/ FiO 2	X	X	X	X	X	X	X	X	X	X	X	X	X	X	X	X	X	
WHO Ordinal Scale for COVID-19 c	X	X	X	X	X	X	X	X	X	X	X	X	X	X	X	X	X	X
12-Lead ECG		X	X												X e	X e		
Concomitant medication review	X	X	X	X	X	X	X	X	X	X	X	X	X	X	X	X	X	X
Assessment for AEs		X	X	X	X	X	X	X	X	X	X	X	X	X	X	X	X	X
Randomization		X																
Dosing		X	X	X	X	X	X	X	X	X	X	X	X	X	X			
PK peak g		X			X										X e	X f		

	Screening	Baseline	Treatment													Time of Discharge a	28-Day Follow-up	End of Study Follow-up
Study Day (Window)	Day -3 to -1	Day 1	2	3	4	5	6	7	8	9	10	11	12	13	14/ EOT + 2		Day 28 (±2 days)	Day 57 (±4 days)
			X (Collect PK sample following first NG dosing, if applicable)															
PK trough d, e, f						X									X e	X f		
PGD2 pre-diagnostic sample collection		X																
Viral titers nasopharyngeal h	X	X	X	X	X	X	X	X	X	X	X					X		
Blood for inflammation markers	X		X		X										X	X		
Proteomic, metabolomics, and transcriptomic sample collection		X													X			

Abbreviations: AE = adverse event; FiO2 = fractional inspired oxygen; ECG = electrocardiogram; EOT = end of treatment; NG = nasogastric tube; O2 = oxygen; PGD2 = prostaglandin D2; PK = pharmacokinetic(s)

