### 7.2.6 O2 Saturation/FiO2

The O2 saturation/FiO2 ratio will be collected on the study days as specified in [Table 1](#).

Oxygen saturation will be documented as a representative value at approximately the same time daily and will use a finger pulse oximeter to approximate O2 saturation.

FiO2 values will be obtained at the corresponding time to the O2 saturation values daily. If a subject is receiving supplemental O2 using a device that reports FiO2 values, then the FiO2 value will be reported from the device and recorded in the CRF. However, if there is no FiO2 readout available (e.g., subject is receiving supplemental O2 by nasal prongs), the site will record the method of O2 delivery and the flow rate in liters of O2 per minute (L/min) in the CRF. If the subject is breathing room air, this will be captured in the CRF rather than the O2 delivery flow rate. Note: High Flow Oxygen will only be documented when using a high flow oxygen delivery device that warms and humidifies the oxygen.

The Sponsor will derive the O2 saturation/FiO2 ratio, using accepted standards for converting O2 delivery rates to FiO2 values.

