4.7 Definition of Baseline Values

The baseline value is defined to be the last non-missing assessment prior to randomization. For baseline WHO ordinal scale, if not collected prior to randomization, the earliest collected WHO ordinal scale collected on the same day as randomization will be used as baseline. Pre-randomization assessments on the same day as randomization will be considered the baseline assessment for each of these respective study procedures. Unless otherwise specified, change from baseline calculations for a treatment window assessment will be the applicable treatment window assessment minus the

baseline assessment. If either the treatment window assessment value or the baseline value is/are missing, then change from baseline will be set to missing.

Age in years will be calculated as (date of informed consent – January 01 of year of birth) / 365.2425.

4.8 *Planned Analyses*

The following statistical analyses are planned for this study:

- Unblinded safety analyses for Data Monitoring Committee (DMC): An independent DMC will be utilized throughout the study to monitor patient safety. DMC meetings for safety will be conducted after 33, 100, and approximately 208 subjects complete assessments through the 28-day follow up (Day 28), approximately 14 days after the final dose of study drug. A DMC charter will be developed preceding study initiation and will define DMC processes and meetings, and required report contents.
- Interim analysis: An interim look for safety and primary endpoint will be conducted by the DMC when approximately 208 patients in the ITT population complete assessments through the 28-day follow up (Day 28), approximately 14 days after the final dose of study drug.

When all subjects enrolled under the targeted or adjusted sample size have completed the study through Day 28 (i.e., full study enrolment is completed), the clinical database will be cleaned, frozen, and an assessment of the primary efficacy endpoint and secondary, exploratory, and safety endpoints up to Day 28 in the ITT population will be created. Individuals involved with the conduct of the study will not have access to unblinded data until database lock. Final analysis: final analysis on efficacy and safety will occur after the database is locked.

4.9 *Multiple Comparison/Multiplicity*

No multiplicity adjustment is planned.

5 Study Population and Disposition

5.1 *Analysis Population*

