11.3 Vital signs

Vital signs measurements (including blood pressure, temperature, respiratory rate, pulse rate, SpO₂, and ratio of SpO₂/FiO₂) and change from baseline values will be summarized over time with n, mean, SD, and median, minimum, and maximum. Summaries will be presented by treatment and overall.

Vital signs information will also be provided in a data listing.

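### The daily SpO2/FiO2 ANCOVA leaves out the subject's own baseline ratio, which is already collected and would improve its precision

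*SAP*

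**What the plan says.** SAP 10.2.4 sets one ANCOVA for a list of continuous secondary endpoints, most of them durations. The model is specified "with treatment as a fixed effect and baseline WHO Ordinal Scale score"; the only other covariates named are age group and region. Wilcoxon and t-tests are reported as well, with no mention of a baseline value.

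Daily SpO2/FiO2 (secondary endpoint 15) is on that list. Of this endpoint the section says "The ratio will be analyzed for each day with the value being collected". The response is therefore the observed ratio on each day, not a change from baseline, and the baseline ratio is not a covariate.

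The baseline ratio is available:

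- Protocol Table 1 has a row "O 2 Saturation/ FiO 2" marked at Screening, Day 1 and every treatment day. Protocol 7.2.6 says the "ratio will be collected on the study days as specified in" that table.
- SAP 4.7 supplies a general definition: "The baseline value is defined to be the last non-missing assessment prior to randomization".
- SAP 11.3 already uses it descriptively. The vital signs tables include "pulse rate, SpO₂, and ratio of SpO₂/FiO₂) and change from baseline values will be summarized over time".

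SAP 4.3 gives the baseline WHO score two levels, 3 or 4. Level 3 is hospitalized without oxygen; level 4 is any oxygen by mask or prongs.

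**The concern.** The baseline value of a continuous measure is usually among the best predictors of its later values. Leaving it out has two consequences. Residual variance is larger than it need be, so the confidence interval is wider on any day when baseline still predicts the ratio. In addition, any chance difference between arms in baseline oxygenation within a WHO level passes into the treatment estimate uncorrected.

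The SAP is also uneven. Its descriptive safety table relates this ratio to the subject's own baseline, while the efficacy comparison of the same ratio does not. The neighbouring endpoint in SAP 10.2.3, the WHO score, is analysed as a change.

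At stake is the precision of one secondary comparison. If baseline oxygenation proves imbalanced, there would also be pressure to choose an adjusted model after seeing the data.

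**Working it through.** **Plan figure.** The documents give no SD, correlation, effect size or power for SpO2/FiO2, so there is nothing to reproduce for this endpoint. The one stated sample size, 312, belongs to the primary endpoint. It does reproduce: 31% against 15%, two-sided 5%, 90% power, with continuity correction, gives 156 per arm, and exact Fisher power is 0.905. It does not bear on this point.

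**How coarse is the WHO covariate?** Inputs are the FiO2 table in SAP 10.2.4, an SpO2 of 94% (assumed, the same throughout) and room air at FiO2 0.21 (assumed).

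- Level 3, room air: 94/0.21 = 448
- Level 4, cannula at 1 L/min: 94/0.24 = 392
- Level 4, cannula at 6 L/min or more: 94/0.44 = 214
- Level 4, reservoir mask above 10 L/min: 94/1.00 = 94

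Level 4 can therefore span 392/94 = 4.2-fold at the table's extremes, or 392/214 = 1.8-fold on nasal cannula alone. The covariate treats all of these subjects alike.

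**What does omission cost?** Let r be the partial correlation of the baseline ratio with the Day-d ratio, given WHO score, age group and region. Adding baseline multiplies the residual variance by 1 − r² and the standard error by √(1 − r²). The planned model thus loses a share r² of the information. Calibrating an effect to 80% power under the planned model, power with baseline added is Φ((1.960 + 0.842)/√(1 − r²) − 1.960). None of these ratios depends on N.

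| r (assumed) | Information lost, r² | SE factor | SE reduction | Power, from 80% |
|---|---|---|---|---|
| 0.3 | 9% | 0.954 | 5% | 83.6% |
| 0.5 | 25% | 0.866 | 13% | 89.9% |
| 0.7 | 49% | 0.714 | 29% | 97.5% |

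The loss passes one half only when r² > 0.5, that is, r > 0.707.

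**How much does WHO score already recover?** As an illustration, suppose WHO score acts only through the baseline ratio and explains a share s of its variance. With marginal correlation ρ, the loss is ρ²(1 − s)/[ρ²(1 − s) + 1 − ρ²]. For ρ = 0.7:

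- s = 0: 0.49/1.00 = 49%
- s = 0.25: 0.3675/0.8775 = 42%
- s = 0.50: 0.245/0.755 = 32%
- s = 0.75: 0.1225/0.6325 = 19%

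The WHO term recovers part of the loss. How much depends on a baseline distribution that the documents do not give.

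**The case against.** The strongest reply is that little depends on this. The estimate is unbiased under randomization. The endpoint is one of 18 secondary endpoints; Protocol 8.4 designates none as key and applies no multiplicity correction, and SAP 10.2.4 itself calls these analyses exploratory. Sample size, interim rule and primary analysis are untouched, and the model already adjusts for oxygen use through the WHO score. All of that stands, and it limits how much weight the point carries. It does not explain why a collected baseline of the same measure should be left out of a between-arm test.

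A second reply is that the four-fold range is a worst case. This also stands. The 94% in inclusion criterion 6 is a room-air limit, not a value on oxygen, and criterion 7 excludes subjects in respiratory failure, so it is uncertain how many enter near FiO2 1.00. The range shows what the table allows, not what was enrolled. The cannula-only range is the more cautious illustration.

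A third reply is that the change is not free. SAP 4.7 gives a same-day fallback for a missing baseline WHO score but none for SpO2/FiO2, and SAP 10.2 imputes nothing for secondary endpoints unless specified. A subject without a pre-randomization ratio would drop out of an adjusted model. Some baseline ratios would also rest on FiO2 estimated from flow rate, which adds measurement error and weakens the covariate. These points call for a missing-baseline rule, not for leaving the covariate out.

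**Conclusion.** The omission is clear from the text: the efficacy model for daily SpO2/FiO2 lacks the baseline ratio, which is collected and used elsewhere in the SAP. The consequence is lost precision, and chance baseline imbalance left uncorrected, in one secondary endpoint. The loss is r² of the information: 9%, 25% or 49% for assumed partial correlations of 0.3, 0.5 or 0.7. Those values are assumptions. The correlation would be expected to weaken with time from baseline, so the gain is probably largest on early days.

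A reader might infer that the planned model throws away most of the available precision. The documents do not support that. It needs a partial correlation above 0.707 after adjustment for WHO score, age group and region, and nothing in the protocol or SAP shows one. Nor should the point be read as a claim of bias: over repeated randomizations the planned estimate is correct on average.

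**What to change.** In SAP 10.2.4, for the SpO2/FiO2 endpoint only, add baseline SpO2/FiO2 as a continuous covariate alongside baseline WHO score, age group and region. Use the SAP 4.7 definition of baseline and the same FiO2 conversion table as for later days. With baseline in the model, the treatment contrast is the same whether the response is the raw ratio or its change, so the response need not be altered.

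Also state how a missing baseline ratio is handled so that no subject is lost, for example by single imputation of the covariate blind to treatment. Leave the duration models in that section as they are.

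The cost is one degree of freedom and the missing-baseline rule; no new data are needed. The change should be written in before unblinding, so that the covariate is not chosen in the light of an observed imbalance.
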